## KEY POINTS

- Conservative feeding therapies are thought to modify GERD symptoms and its consequences. However, in this randomized controlled trial in convalescing neonatal ICU infants with GERD symptoms, when controlling for preterm or full-term birth and severity of esophageal acid reflux index, the effectiveness of acid suppression plus a feeding modification bundle (volume restriction, intra- and post- prandial body positions, and prolonged feeding periods) vs. acid suppression alone, administered over a 4-week period was not superior in improving symptom scores or feeding outcomes.
- Restrictive feeding strategies are of no impact in modifying GERD symptoms or clinically meaningful outcomes. Further studies are needed to define true GERD and to identify effective therapies in modifying pathophysiology and outcomes.
- The improvement in symptoms and feeding outcomes over time irrespective of feeding modifications may suggest a maturational effect. This study justifies the use of placebo controlled randomized clinical trial among NICU infants with objectively defined GERD.

## **ABSTRACT**

**OBJECTIVE:** To test the hypothesis that a feeding-bundle concurrent with acid-suppression is superior to acid-suppression alone in improving gastroesophageal reflux disease (GERD) attributed-symptom scores and feeding outcomes in neonatal ICU infants.

**METHODS:** Infants (N=76) between 34-60 weeks' postmenstrual age with acid reflux index>3% were randomly allocated to study (acid suppressive therapy + feeding bundle) or conventional (acid suppressive therapy only) arms for 4 weeks. Feeding bundle included: total fluid volume <140 ml/kg/day, fed over 30 min in right lateral position, and supine postprandial position. Primary outcome was independent oral feeding and/or  $\geq 6$ -point decrease in symptom score (I-GERQ-R). Secondary outcomes included growth (weight, length, head circumference), length of hospital stay (LOHS, days), airway (oxygen at discharge), and developmental (Bayley scores) milestones.

**RESULTS:** Of 688 screened: 76 infants were randomized and used for the primary outcome as intent-to-treat, and secondary outcomes analyzed for 72 infants (N=35 conventional, N=37 study). For study vs conventional groups, respectively: a) 33%(95% CI, 19%-49%) vs 44%(95% CI, 28%-62%), p=0.28 achieved primary outcome success, and b) secondary outcomes did not significantly differ (p>0.05).

**CONCLUSIONS:** Feeding strategy modifications concurrent with acid suppression are not superior to PPI alone in improving GERD symptoms or discharge feeding, short-term and long-term outcomes.

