short- and long-term clinical outcomes among infants treated concurrently over 4 weeks with PPI with randomly assigned feeding strategy modifications while controlling for gestational maturity (pre-term or full-term at birth) and severity of esophageal ARI (3-7%, >7%). Our *hypothesis* was that the study approach (acid suppression, modified feeding volume, duration, and position) was superior in achieving independent oral feeding or a 6-point reduction in I-GERQ-R vs the conventional (acid suppression alone) feeding approach.

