## **STUDY INTERVENTIONS**

### **Interventions**

Providers employ uniform feeding and nutritional practices in our NICU infants as per our standardized guidelines, which applies to nutrient and volume modifications. However, upon randomization and allocation, individual protocols are complied with. Upon completion of screening, enrollment and randomization, the assigned feeding management strategy was relayed to parents and the medical team. Subjects in both arms received omeprazole off label, as a therapeutic choice (27, 28) at a recommended dose of 0.75 mg/kg/dose BID (15, 27, 29). The conventional approach was to not adjust provider recommended feeding strategies (i.e. fed in any

position, duration, volume, and postprandial position). The study approach utilized a modified feeding strategy including: a) feeding in the right lateral position to facilitate intra-prandial gastric emptying (30), b) feeding duration of at least 30 min utilizing pacing when orally fed to ensure completion of prescribed volumes or via pump to ensure steady delivery of milk if gavage-fed (21), c) supine postprandial position (31), and d) limiting total feeding volume to  $\leq 140$  ml/kg/day (21).

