to randomization would have resulted in all patients being treated based on subjective, non-specific symptoms alone. Owing to the strict inclusion and exclusion criteria of this RCT, those with indeterminate and abnormal ARI were treated with a PPI. In the future, a careful RCT that tests the utility of PPI treatment for confirmed acid-GERD by allocating patients to either limited PPI treatment or placebo is indicated to determine whether PPI treatment is needed. The effectiveness of our short-term use of PPI for 4 weeks to improve GERD-attributable symptoms should be tested in future trials. Effect of esophageal acid exposure and therapies on primary mechanistic outcomes of esophageal motility and symptom causation will be addressed in future reports. 5) In routine clinical practice, feeding volumes are modified and alterations in feeding positions are used to manage symptoms. Our study did not show any differences in the outcomes with feeding- and position modifications. Furthermore, volume restriction had no influence on the study outcomes. The improvement in symptoms and feeding outcomes over time irrespective of PPI or feeding modifications may suggest a maturational effect.

It is important to note that major mechanisms of GER, i.e. transient LES relaxation is the major reason for any reflux events- both acid or non-acid substrate. Our therapeutic target was acid reflux index in this study via PPI, feeding volumes, and positional changes. Given that acid GER can also have weakly or non-acid either before or after PPI therapy, and that there were no differences in outcomes between the two groups, we speculate that neither PPI, feeding volume, or positional changes modify the studied indices or symptoms. Maturation under optimal conditions of good nutrition along with placebo-controlled trials are needed to answer the importance of weakly acid or non-acid GER, which would require a multicenter trial with a large group of infants with appropriate physiologic diagnostic testing.

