**Table 2. Primary and Secondary Clinical Outcomes and Compliance Measures**

Primary Outcome (intent-to-treat analysis)	Overall (N = 76)	Conventional (N = 36)	Study (N = 40)	P-value
A priori clinical outcome Success, n (%)	29 (38)	16 (44)	13 (33)	0.28
Secondary Outcomes	Overall (N = 72)	Conventional (N = 35)	Study (N = 37)	P-value
I-GERQ-R decrease by 6 – n (%)	24/65 (37)	11/31 (35)	13/34 (38)	0.82
Feeding Outcome at Time 2 – n (%)				0.26
PO	51 (71)	27 (77)	24 (65)	
Transition (PO + Tube)	18 (25)	8 (23)	10 (27)	
Tube	3 (4)	0 (0)	3 (8)	
Length of hospital stay – days	108 [82 - 128]	108 [83 - 125]	98 [81 - 132]	0.89
Hospital stay Inception to Discharge – days	25 [11 - 45]	23 [3 - 39]	27 [16 - 47]	0.26
Weight Growth Velocity (GV) – g/day	27.1 (9.4)	26.5 (7.2)	27.6 (11.1)	0.64
Length GV – cm/day*	0.1 (0.1)	0.1 (0.1)	0.1 (0.1)	0.88
Head Circumference GV – cm/day*	0.1 [0.0 - 0.1]	0.1 [0.0 - 0.1]	0.1 [0.0 - 0.1]	0.87
Feeding Method at Discharge – n (%)				0.32
PO	54 (75)	29 (83)	25 (68)	
Transition (PO + Tube)	14 (19)	5 (14)	9 (24)	
Tube	4 (6)	1 (3)	3 (8)	
Oxygen Requirement at discharge – n (%)	16 (22)	9 (26)	7 (19)	0.49
Compliance to Feeding Methods				
Total Fluid Volume (TFV)				
TFV at Inception- #	N/A	150 [147, 152]	150 [149, 156]	0.8
TFV at Time 2- #	N/A	143 [134, 148]*	133 [126, 137]*	<0.001
# days TFV ≤ 140 / kg / day	N/A	10 [2, 26]	22 [11, 31]	0.005
TFV compliance (TFV <140/kg/d for >75% of time)	N/A	9 (26)	27 (73)	<0.001
Position				
Feeding Position, RSL, %	N/A	5 [1, 17]	78 [12, 94]	<0.001
Feeding in RSL >75% of the time, %	N/A	0 (0)	21 (57)	<0.001
Supine Position Post-Prandial, %	N/A	50 [40, 66]	87 [74, 96]	<0.001
Supine Position Post-prandial >75% of the time, %	N/A	7/34 (21)	27/36 (75)	<0.001
Feeding Duration				
% time feed duration >30 min, %	N/A	4 [0, 37]	15 [0, 69]	0.15
Feeding Duration at Inception, min	N/A	23 [17, 41]	30 [19, 34]	0.64
Feeding Duration at Time 2, min	N/A	23 [18, 28]	26 [20, 30]	0.15
Long-term Follow-up†				
Feeding Method at 6 months – n (%)				0.65
PO	36/50 (72)	21/27 (78)	15/23 (65)	
Transition (PO + Tube)	10/50 (20)	4/27 (15)	6/23 (26)	
Tube	4/50 (8)	2/27 (7)	2/23 (9)	
Feeding Method at 1 year – n (%)				0.11
PO	37/44 (84)	20/22 (91)	17/22 (77)	
Transition (PO + Tube)	4/44 (9)	0/22 (0)	4/22 (18)	
Tube	3/44 (7)	2/22 (9)	1/22 (5)	
CCABSID-III				
Cognitive Score <80 – n (%)	9/44 (21)	5/23 (22)	4/21 (19)	1.00
Cognitive Score – #	95 [90 - 105]	100 [90 - 105]	90 [90 - 100]	0.11

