## 1.0 Study Summary

Study Title	Pathophysiology of Aerodigestive Reflex in Infants: GERD Management Trial
Study Design	Single center randomized control trial
Primary Objective	To compare two feeding approaches and their effect on clinical outcomes in infants with proven Gastroesophageal Reflux Disease (GERD)
Secondary Objective(s)	To determine the pathophysiological mechanism of success or failure to either therapy, we will test the hypothesis and validate results from the preliminary data by utilizing our diagnostic tools to identify differences between the two study arms in regards to: aerodigestive reflexes, esophageal clearance mechanisms, neuromotor markers of swallowing, and pH-Impedance-symptom indices.
Research Intervention(s)/ Investigational Agent(s)	Both groups will have esophageal manometry studies followed by randomization into two groups, Conventional and Study. The conventional group allows for unrestricted feeding volumes with no time limit, feeds given in any position and random post prandial feeding positions. The study group will have permissive feeding volume restrictions, feeding duration of at least 30 minutes, feeding given in right side lying, and supine post prandial position. Both groups will be treated with omeprazole per NCH NICU guidelines

IND/IDE #	N/A
Study Population	Infants admitted to the NICU at NCH and referred to the Neonatal and Infant Feeding Disorders program for evaluation of Gastroesophageal reflux Disease (GERD)
Sample Size	120
Study Duration for individual participants	5 weeks
Study Specific Abbreviations/ Definitions	GMT (GERD Management and Therapy Trial) RSL- right side lying ARI –Acid reflux index PMA= (Gestational age at birth + chronologic age)

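### The comparator is labelled acid suppression alone, but it was omeprazole with provider-directed feeding, and the conclusions go beyond that contrast

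*Combined protocol and SAP*

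**What the plan says.** **The label.** The Abstract's methods call the comparator "conventional (acid suppressive therapy only) arms for 4 weeks". The hypothesis at the end of the Introduction sets the bundle "vs the conventional (acid suppression alone) feeding approach". The Key Points and the Discussion (salient features, item 3) use the same label. The Abstract concludes: "Feeding strategy modifications concurrent with acid suppression are not superior to PPI alone".

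**The definition.** Study Interventions states: "The conventional approach was to not adjust provider recommended feeding strategies". It adds that position, duration, volume and postprandial position were all left open. Protocol section 1.0 (Study Summary) agrees: the conventional group "allows for unrestricted feeding volumes with no time limit, feeds given in any position and random post prandial feeding positions". Neither place bars any element of the bundle. Study Interventions also says that the assigned strategy was relayed to parents and the medical team, so those choosing the conventional-arm feeding knew the allocation.

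**The background.** The Discussion (strengths, item 5) states: "In routine clinical practice, feeding volumes are modified and alterations in feeding positions are used to manage symptoms".

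**What is concluded.** The same Discussion item says: "Furthermore, volume restriction had no influence on the study outcomes". The Key Points deny that restrictive feeding has any effect on symptoms or meaningful outcomes. Item 2 of the Conclusion denies feeding modification any part in reducing symptoms or improving the primary outcome.

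**The concern.** The label and the definition describe two different comparators. Acid suppression alone implies controls with no feeding modification. The definition describes usual care, in which a provider may reduce volume or change position, and the report says that providers do so routinely. If some controls received parts of the bundle, the trial compares an assigned bundle with provider-directed feeding. It does not compare feeding modification with none.

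What is at stake is how the null result is read. Someone who takes the label at face value will conclude that restricting volume or changing position adds nothing to a PPI. The trial did not test that. The statements about single components go further still, because no component was randomised separately.

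**Working it through.** **Step 1. Overlap in the conventional arm.** Inputs are from Table 2, compliance block, with N=35 conventional and N=37 study unless another denominator is printed. The volume row is "TFV compliance (TFV <140/kg/d for >75% of time").

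| Component | Conventional | Study | Separation |
|---|---|---|---|
| Volume standard met | 9/35 = 25.7% | 27/37 = 73.0% | 47.3 points |
| Supine after feeds >75% of the time | 7/34 = 20.6% | 27/36 = 75.0% | 54.4 points |
| Right-side feeding >75% of the time | 0/35 = 0% | 21/37 = 56.8% | 56.8 points |
| Feeding duration at Time 2, median | 23 min | 26 min | P=0.15 in Table 2 |

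The printed percentages reproduce. The uncorrected chi-square test gives P=0.00006 for volume and P=0.000005 for supine posture, both consistent with the printed <0.001. The exact 95% CI for 9/35 is 12.5% to 43.3%.

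Table 2 also gives the conventional arm a median of 10 days [2, 26] at or below 140 ml/kg/day, against 22 [11, 31] in the study arm, and Time-2 median volumes of 143 against 133 ml/kg/day. The limit is written as below 140 in the Abstract and the compliance row, and as at or below 140 elsewhere. Those passages should be reconciled, but the overlap does not depend on it.

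The arms therefore separated clearly on three components and not significantly on the fourth. The conventional arm was not free of feeding modification on volume or supine posture. No conventional infant reached the right-side threshold, so none met every component at the table's thresholds.

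**Step 2. The primary result.** Inputs are from Table 2: study 13/40, conventional 16/36. The uncorrected chi-square test gives P=0.284, which reproduces the printed 0.28.

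- Difference, study minus conventional: 0.325 - 0.444 = -0.119.
- Standard error: sqrt(0.325 x 0.675/40 + 0.444 x 0.556/36) = 0.111.
- Wald 95% CI: -0.119 ± 1.96 x 0.111, about -34 to +10 points.

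**Step 3. Claims against the contrast.** Randomisation assigned the whole bundle or provider-directed feeding. The intention-to-treat difference estimates that contrast. A statement about PPI alone needs controls without feeding modification, and Step 1 shows that they were not. A statement about volume restriction by itself needs volume to have been varied with the other components held fixed. It was not: right-side feeding and supine posture moved with it.

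**The case against.** The strongest reply is that this is shorthand in a report whose design is openly stated. The protocol's primary objective is to compare two feeding approaches, its sample-size section names standard therapy as the control, Study Interventions defines the arm plainly, and Table 2 already reports component use by arm. Usual care is a legitimate comparator. All of this stands. The fault lies in labelling and interpretation. There is no concealed change of design, and the intention-to-treat analysis is sound for the contrast that was randomised.

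Several stronger readings are tempting, and the documents do not support them.

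- *The overlap hid a real benefit.* Overlap would shrink a benefit towards zero; it would not by itself reverse the sign. The observed difference favours the conventional arm. Nor can the planned 27-point effect be scaled down by the 47-point volume separation. That effect was set against about 40% success on standard therapy (protocol section 3.3), which may already include usual-care feeding changes, so the scaling would discount twice.
- *A complier estimate for volume would settle it.* Dividing the difference by the volume separation requires that randomisation acted only through volume. Table 2 shows that it also moved right-side feeding (57% against 0%) and supine posture (75% against 21%).
- *Controls received the bundle's elements as rescue.* No reasons for feeding changes are reported. An infant of 3.5 kg (Table 1) kept on 150 x 3.5 = 525 ml/day and gaining 26.5 g/day (Table 2) would weigh 3.5 + 28 x 0.0265 = 4.24 kg after 28 days, and 525/4.24 is about 124 ml/kg/day. A fall in ml/kg can therefore occur without deliberate restriction. The report supports supine posture by citing infant safe-sleep recommendations, so its use in controls may be routine care.
- *Conventional-arm volume fell significantly.* The compliance section reports a reduction in both groups, but its significance statement concerns the study group. Table 2 prints no within-arm P value, and the only printed footnote for the asterisk is about a missing value.

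**Conclusion.** The point holds as one of labelling and over-interpretation. The comparator was omeprazole with provider-directed feeding. About a quarter of its infants (26%, exact 95% CI 12.5% to 43.3%) met the study arm's volume standard and about a fifth (21%) met the supine threshold, while none met the right-side threshold.

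The trial supports this statement: an assigned bundle was not shown to be superior to provider-directed feeding, with a difference of -11.9 points (95% CI about -34 to +10). It does not support conclusions against a PPI alone, or conclusions that volume restriction or feeding modification in general is without effect. The direction of the result means that the overlap should not be offered as an explanation for a missed benefit.

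This rests on the counts printed in Table 2. Receipt of the full bundle by individual infants is not reported.

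**What to change.** 1. Rename the comparator *omeprazole with provider-directed feeding* in the Key Points, the Abstract, the hypothesis in the Introduction, and item 3 of the salient features in the Discussion.
2. Beside the primary result, report component use by arm (volume 26% against 73%, supine 21% against 75%, right-side 0% against 57%, duration P=0.15) together with the difference of -11.9 points and its interval.
3. Limit the conclusions in the Key Points, the Abstract and the Conclusion to assigned bundle versus provider-directed feeding.
4. Delete the Discussion sentence stating that volume restriction did not influence outcomes. Item 4 of the salient features makes the same kind of component claim and needs the same limit.

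No feeding rule changes and no new data are needed. All the counts are already in Table 2, and the interval follows from them. The cost is a narrower conclusion.

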## OUTCOME MEASURES

The *a priori primary end-point* was achieving independent oral feeds and/or a six-point decrease in I-GERQ-R score at 5 weeks or sooner, whichever was earliest at discharge. *To clarify further, there were 2 scenarios:* 1) Among infants who were transitioning to oral feeds (gavage fed) at inception: success was defined as achieving full oral feeds or a  $\geq 6$ -point decrease from baseline I-GERQ-R. 2) Among infants who were on full oral feeds at inception, success was determined if full oral feeds were maintained plus a  $\geq 6$ -points decrease from baseline I-GERQ-R. *Secondary end-points* included growth metrics (weight, length and head circumference), supplemental oxygen, economic metrics (LOHS), long-term feeding outcomes at 6 months and 1 year, and developmental outcomes at 2 years (32, 33).

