## STATISTICAL METHODS

Based on our preliminary data, we had planned to enroll 100 patients (50 per group) to detect 27% or higher increase in proportion of success of study group compared to the conventional group with 80% power and overall one-sided  $\alpha$  level of 0.025. One interim futility analysis was planned at about 50% information prior to the final analysis at 100% information, corresponding to 50 and 100 evaluable patients, respectively. The boundary was determined using Lan-DeMets spending functions to simulate O'Brein-Fleming boundaries(34). Using the target proportion of success, the boundary at the futility analysis was  $p>0.297$ .

Seventy-six infants were randomly assigned till the end of funding for this study and were included in the analysis of demographics and clinical characteristics (**Fig 1, Table 1**) and primary outcome by intent-to-treat. If a patient dropped out before the end of study and no symptom score was evaluable, we treated the patient as a failure for the primary outcome by intention-to-treat. Secondary outcome analysis was performed for 72 subjects (**Fig 1**). Futility boundary was not reached at interim analysis of 50 patients ( $p=0.1 < 0.297$ ) and accrual was continued with DSMB approval. Summary statistics were calculated for patient demographics and clinical characteristics for final analysis. Success rate in achieving PO or reduction in the I-GERQ-R by 6-points was calculated with 95% confidence interval and compared using chi-square test between the conventional and study groups (primary outcomes) for the intention-to-treat and treat-as-treated analyses. Fisher's exact or chi-square test were used to compare other categorical secondary outcomes including feeding method and supplemental oxygen between the groups. Shapiro-Wilk test for normality was used for the continuous outcomes. Paired t-tests or Wilcoxon singed-rank

tests were used to assess changes in growth velocity and feeding therapy characteristics between time-1 and time-2. Two sample t-tests or Wilcoxon rank-sum tests were used to compare these continuous outcomes between conventional and study groups. Median (interquartile range [IQR]), mean (SD), or % was reported, unless stated otherwise.  $P$  values  $<0.05$  were considered statistically significant, and SAS version 9.4 (SAS, Inc, an IBM Company, Chicago, IL) was used.

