## **CONCLUSION**

We addressed the current practice controversies in this clinical trial: 1) Screening and identifying acid-GERD objectively is possible in symptomatic infants prior to any pharmacotherapy. 2) Feeding strategy modification (fluid restriction, positional changes, prolonged feeding duration) has no role in decreasing reflux-type symptoms or in improving the primary outcome of achieving independent oral feeds and/or a six-point decrease in I-GERQ-R score. 3) No difference in the prevalence of chronic lung disease was noted between the groups. 4) I-GERQ-R scores decreased across time regardless of treatment group allocations that strongly

support maturational effect. However, we did not detect an effect on *a priori* short-term or long-term outcomes following randomized allocations. As restrictive feeding strategies do not make a difference, placebo-controlled clinical trials in a larger cohort of convalescing NICU infants with objectively determined newer GERD criteria must be addressed in future trials.

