## 4.0 Study Endpoints

- Primary Outcome
  - **Clinical outcome of feeding success for those infants transitioning to oral feeds at inception.**
    - The primary endpoint is the feeding success defined as achieving full oral feeds (defined as no need for tube feeds to maintain hydration and nutrition) and/or a  $>/=$  6-point decrease from baseline I-GERQ-R. The time frame is up to 5 weeks after enrollment.
  - **Clinical outcome of feeding success for those infants on full oral feeds at inception.**
    - The primary endpoint is the feeding success defined as maintaining full oral feeds and a  $>/=$  6-point decrease from baseline I-GERQ-R. The time frame is up to 5 weeks after enrollment.
- Secondary Outcomes
  - Clinical Outcomes
    - Length of hospital stay
    - Growth outcomes during the study period and up to 1 year
    - Independent feeding skills over time up to 1 year
    - Respiratory support during the study period and at discharge
    - Developmental outcomes with Bayley's scores at 2 years
    - Individual differences in I-GERQ-R questionnaire
  - Motility Outcomes
    - Mechanisms of aerodigestive clearance and esophageal provocation are evaluated based on esophageal motility studies at inception and after 5 weeks.
  - pH Impedance outcomes
    - 24-hour pH impedance results at inception of study and then 5 weeks later after treatment completed

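### The primary outcome is stated under two different rules; the reported 16/36 and 13/40 are impossible under one and do not match Table 3 under the other

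*Combined protocol and SAP*

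**What the plan says.** Four places in the article give the primary outcome as one rule, with no reference to how the infant was fed at inception:

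- Abstract: "Primary outcome was independent oral feeding and/or" a fall of at least 6 points in the symptom score.
- Introduction (hypothesis): the study approach "was superior in achieving independent oral feeding or a 6-point reduction in I-GERQ-R".
- Statistical Methods, describing what was computed and tested: "Success rate in achieving PO or reduction in the I-GERQ-R by 6-points was calculated".
- Conclusion: "primary outcome of achieving independent oral feeds and/or a six-point decrease in I-GERQ-R score".

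Two places split the rule. Outcome Measures opens with the *and/or* form and then sets out two scenarios. Infants moving from tube to oral feeds succeed on full oral feeds *or* a fall of at least 6 points. For infants already on full oral feeds, "success was determined if full oral feeds were maintained plus a" fall of at least 6 points. Protocol section 4.0 (Study Endpoints) agrees for the second group: "The primary endpoint is the feeding success defined as maintaining full oral feeds and a" fall of at least 6 points.

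Table 2 reports intention-to-treat success in 16/36 (44%) conventional and 13/40 (33%) study infants, p = 0.28.

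**The concern.** About half the trial was orally fed at inception (37 of 76 in Table 1), so the choice of rule largely fixes the success rate. Among the orally fed infants in Table 3, 33 of 34 succeed if either condition is enough, but only 9 of the 28 with a score succeed if both are needed.

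The Statistical Methods sentence is the one an analyst or a replicator would follow, and as written it yields a different primary result. A reader of the abstract alone would take 33% versus 44% to be the share with oral feeding or symptom improvement, which the article's own oral feeding counts rule out. If the split rule does not reproduce the figures either, the trial's main result has no stated definition behind it.

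**Working it through.** **Reproducing the reported figures.** 16/36 = 44.4%, exact 95% interval 27.9% to 61.9%. 13/40 = 32.5%, exact interval 18.6% to 49.1%. Uncorrected chi-square: 76 × (16×27 − 20×13)² / (36×40×29×47) = 1.15, p = 0.284. All agree with the printed values, so the percentages, intervals and p-value follow from the counts 16 and 13. The question is where those counts come from.

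**Inputs from Tables 2 and 3** (conventional, study):

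- Full oral feeding at Time 2 (Table 2): 27 of 35, 24 of 37.
- Fall of at least 6 points (Table 2): 11 of 31, 13 of 34. So 35 − 31 = 4 and 37 − 34 = 3 infants have no evaluable change.
- Tube-fed at inception (Table 3, N = 18, 20): oral feeding 11, 7; score fall 7 of 17, 8; either 14, 13; both 4 of 17, 2.
- Orally fed at inception (Table 3, N = 17, 17): maintained 16, 17; score fall 4 of 14, 5 of 14; either 16, 17; both 4 of 14, 5 of 14.

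In the machine-read text of Table 3 the tube-fed counts sit one line below their labels, an artefact of reading the PDF. The realignment used here checks out:

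- Oral feeding: 11 + 16 = 27 and 7 + 17 = 24, as in Table 2.
- Score fall: 7 + 4 = 11 and 8 + 5 = 13, as in Table 2.
- Either, tube-fed: 11 + 7 − 4 = 14 and 7 + 8 − 2 = 13.

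**Unsplit rule.** From Table 3: (14 + 16)/36 = 30/36 = 83% and (13 + 17)/40 = 30/40 = 75%; chi-square 0.79, p = 0.37. As a lower bound from oral feeding alone: 27/36 = 75% and 24/40 = 60%. Removing every infant without an evaluable score, as if all were orally fed and all were failed: (27 − 4)/36 = 23/36 = 64% and (24 − 3)/40 = 21/40 = 52.5%. Pooled over arms, that is at least 44/76 against the reported 29/76. Oral feeding at discharge is higher still (29 and 25), so a later assessment does not help.

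**Two-scenario rule.** Take *either* for tube-fed and *both* for orally fed infants: (14 + 4)/36 = 18/36 = 50% and (13 + 5)/40 = 18/40 = 45%; chi-square 76 × (18×22 − 18×18)² / (36×40×36×40) = 0.19, p = 0.66. Only one tube-fed infant lacks a score, in the conventional arm. Failing that infant gives 17/36 = 47%. No tube-fed study infant in Table 3 lacks a score, so 18/40 does not move.

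| Rule | Conventional (of 36) | Study (of 40) | Difference, study − conventional |
|---|---|---|---|
| Reported | 16 (44%) | 13 (33%) | −12 points |
| Unsplit | 30 (83%) | 30 (75%) | −8 points |
| Two-scenario | 18 (50%) | 18 (45%) | −5 points |
| Two-scenario, unscored tube-fed infant failed | 17 (47%) | 18 (45%) | −2 points |
| Both conditions for everyone | 4 + 4 = 8 | 2 + 5 = 7 | |
| Score fall alone | 11 | 13 | |

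No row built from Table 3 gives 16 and 13 together. The four randomised infants outside Table 3 (1 conventional, 3 study) are counted as failures throughout; counting any of them as successes would only raise the totals.

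**The case against.** The strongest reply is that the rule is defined. Protocol section 4.0 and Outcome Measures both give the split, and Outcome Measures uses the *and/or* phrase as a lead-in to the two scenarios, so *and/or* in the abstract and conclusion can be read as shorthand. The protocol's own statistical section contains no unsplit sentence. The design figures point the same way: they assume about 40% success on standard therapy, and a 27-point gain on 83% would exceed 100%.

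Most of this stands. A reader might infer that the documents explicitly apply the *or* rule to every infant. They do not; that reading comes from the missing split in four places. A reader might also infer that the endpoint was never defined, and the two endpoint sections show otherwise. What does not stand is the defence of the Statistical Methods and the hypothesis. Both use a plain *or* with no pointer to the scenarios, and the first is the sentence that says what was calculated.

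The shorthand reading also leads to a second inference, that 33% versus 44% is simply the two-scenario result and only the wording needs care. Table 3 does not support that: the pooled two-scenario count is at least 35 against the reported 29.

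It is also fair to say that the trial's conclusion does not hang on this. The p-value is 0.28 as reported, 0.37 under the unsplit rule and 0.66 under the two-scenario rule, and each numerically favours the conventional arm.

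**Conclusion.** The point holds as an inconsistency between sections together with a headline result that the published tables do not reproduce. The unsplit rule cannot produce 16/36 and 13/40: Table 3 gives 30/36 and 30/40, and the harshest handling of missing scores still leaves at least 23/36 and 21/40. The two-scenario rule gives 18/36 (or 17/36) and 18/40, so the reported counts are lower by 1 or 2 conventional and 5 study infants.

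Three stronger statements are tempting and should not be made:

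- That success under the unsplit rule could not fall below the published oral feeding rates of 77% and 65%. Those use 35 and 37 infants; over the 36 and 40 randomised, the same counts give 75% and 60%, or less if unscored infants are failed.
- That all 37 infants orally fed at inception would be near-automatic successes. Table 3 covers 34 of them, and dropouts without a score count as failures.
- That the non-superiority conclusion is wrong. It is unchanged under the reported counts, the unsplit rule and the two-scenario rule.

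The result rests on the realigned rows of Table 3, which agree with Table 2. The participant flow figure is not available, so the handling of the four infants outside Table 3 cannot be seen, but it does not affect the pooled lower bound. The documents do not show whether the discrepancy lies in Table 2, in Table 3, or in an assessment time or missing-score rule that is not stated.

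**What to change.** 1. State the two-scenario rule of Outcome Measures and protocol section 4.0 in the Statistical Methods, and carry it into the abstract, hypothesis and conclusion.
2. Recompute the intention-to-treat primary under that rule.
3. State the assessment time and the handling of missing scores that lie behind 16 and 13, including how an orally fed infant with no score is classified.
4. Reconcile Table 2 with Table 3, and correct the headline percentages, confidence intervals and p-value if they change.

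The cost is a re-tabulation of data already collected and locked, and possibly a changed headline figure. It is more than a wording edit, because adding the two-scenario definition to the present numbers would attach a rule that the tables do not reproduce. No new data are needed.
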